9.3 POPULATIONS FOR ANALYSES

9.4 STATISTICAL ANALYSES

9.4.1 GENERAL APPROACH

To analyze descriptive statistics we will use frequencies, mean, and standard deviation.

9.4.2 ANALYSIS OF THE PRIMARY ENDPOINT(S)

We will used mixed-effect models to Repeated measures ANOVA.

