9 STATISTICAL CONSIDERATIONS

9.1 STATISTICAL HYPOTHESES

- Primary Efficacy Endpoint(s): We hypothesize that participants will increase their average steps/day from
 baseline to the initial adoption of the active intervention, there will be a significant difference in average
 steps/day from baseline to the last week of the active intervention, there will be a significant difference in
 average steps/day from baseline to the follow-up phase post-active intervention, participants will
 experience a decrease in average steps/day each day from the start of the 8-week intervention to the
 end. two to week eight.
- Secondary Efficacy Endpoint(s): We hypothesize participants will increase their feelings of social support, self-efficacy, and outcome expectations, and decrease their feeling of social isolation from baseline to post-active intervention. We hypothesize this will be an acceptable multilevel mHealth intervention among older adults living in a retirement community.

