9.2 SAMPLE SIZE DETERMINATION

To achieve 80% power to detect a 1,750 step difference in step counts between the pre- and post-intervention periods, with a standard deviation of 2,000 steps and a significance level of 0.05, we are required to enroll at least 42 participants. If we add an additional 25% for possible drop outs, we will need to enroll at least 50 participants into the older adult group.

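### The one sentence on the primary analysis does not identify a single model: its ANOVA reading drops incomplete participants and gives no daily slope by default, and a random-intercept-only reading can inflate the slope test's error

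*Combined protocol and SAP*

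**What the plan says.** Section 9.4.2 reads in full: "We will used mixed-effect models to Repeated measures ANOVA". Nothing else describes the primary model. Section 9.3 (populations) is a heading only, and section 9.4.1 covers descriptive statistics. The plan does not state the outcome unit (day, week or phase), fixed effects, random effects, residual correlation, contrasts or a rule for missing days.

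Section 9.1 sets out four primary hypotheses. The first opens "We hypothesize that participants will increase their average steps/day from" and compares baseline with initial adoption. Two more compare baseline with the last intervention week and with follow-up. The fourth is that participants will "experience a decrease in average steps/day each day from the start of the 8-week intervention to the" end. That sentence finishes with a stray fragment about weeks two to eight, so the slope window is unclear.

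Incomplete data are expected. Section 9.2 says "If we add an additional 25% for possible drop outs, we will need to enroll at least 50 participants into the older adult group", and section 8.1 makes wearing and syncing the monitor an outcome. Section 8.1 also provides minute-level data, so daily counts will exist.

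The synopsis describes 4 days of baseline collection. Section 6.1.1 describes two weeks.

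**The concern.** The two named methods are not interchangeable here. Classical repeated-measures ANOVA needs complete data for each participant and assumes sphericity. Its omnibus test of time does not yield a steps-per-day slope. A mixed model uses all available days, but the standard error of its slope depends on the random effects and residual correlation, and none are stated.

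An analyst could therefore follow section 9.4.2 and choose the participants, the unit and the test after seeing the data. A completer-only analysis is biased if drop-out is related to the change in steps. A random-intercept-only model has no term for people declining at different rates, or for neighbouring days being alike. Either feature makes the slope's standard error too small.

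**Working it through.** **The plan's own figures.** Section 9.2 aims for 80% power for a change of 1,750 steps, taking an SD of 2,000 and alpha 0.05, and concludes "we are required to enroll at least 42 participants". With two-sided alpha assumed, the two-independent-group formula is n per group = 2 × (1.960 + 0.842)² × (2,000/1,750)² = 20.5, so 21 per group and 42 in total. That reproduces 42, though not for a pre-post design. Adding 25% gives 42 × 1.25 = 52.5, or 42/0.75 = 56, rather than 50. Both are separate matters. The stated 50 is used below only as the minimum enrolment.

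**Participants kept by a complete-case ANOVA.**
- Drop-out alone: 50 × 0.75 = 37.5, about 37.
- Days as the ANOVA levels, with days missing independently (assumed rates, no drop-out): 50 × 0.99^56 = 28; 50 × 0.98^56 = 16; 50 × 0.95^56 = 3.
- Phase means as the levels: sporadic missing days cost far less, and the loss stays closer to the drop-out figure.

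**Power with 37 completers.** A paired t test for 1,750 steps has 99.9% power if the SD of change is 2,000. It has 95.6% if the SD of change is 2,828, which is 2,000 × √2 (SD 2,000 at each time, correlation zero).

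**Error of the daily-slope test under a random-intercept-only model.** Assumptions: 56 days, no missing days, true mean slope zero, daily residual SD 2,000 (section 9.2's SD borrowed for scale).
- Sum of squares of day: 56 × (56² − 1)/12 = 14,630.
- With independent residuals and no slope variation, the variance of one participant's slope is 4,000,000/14,630 = 273.4.
- With between-person slope SD τ, the true variance is 273.4 + τ². The model absorbs slope variation into its residual and uses (4,000,000 + τ² × 14,630/55)/14,630.
- Actual two-sided error is 2 × [1 − Φ(1.96 × √(model variance/true variance))]. The number of participants cancels.

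Putting numbers in:
- τ = 10: √(275.2/373.4) = 0.859; 1.96 × 0.859 = 1.68; error 9%.
- τ = 20: √(280.7/673.4) = 0.646; 1.96 × 0.646 = 1.27; error 21%.
- τ = 0, AR(1) 0.2: true variance 401.0, model variance 271.0; ratio of SEs 0.822; error 11%.

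Simulation (50 participants, 2,000 trials per setting, Monte Carlo SE about 0.5 points at 5%) beside the formula:

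| AR(1) | Slope SD 0: formula / simulated | Slope SD 10 | Slope SD 20 |
|---|---|---|---|
| 0 | 5% / 5% | 9% / 9% | 21% / 22% |
| 0.2 | 11% / 12% | 15% / 14% | 25% / 27% |
| 0.4 | 19% / 21% | 23% / 22% | 31% / 31% |

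Over a wider assumed grid (slope SD to 44.8, AR(1) to 0.5) the error ran from about 5% to about 52%. A t test on each participant's own slope, which for balanced data is equivalent to allowing random slopes, stayed between 3.5% and 6.4% throughout.

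**The case against.** **A missing verb.** The sentence may mean a mixed model used to carry out the repeated-measures comparison. On that reading there is no listwise deletion and no sphericity assumption. This is possible, but the text does not settle it, and the random effects, unit and contrasts would still be absent.

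**The inflated error.** A reader might infer that the planned mixed model will give a wrong error rate. The documents do not support that. They never specify a random intercept alone, and they give neither a slope SD nor an autocorrelation. With both at zero the test is nominal. The mean declines of 44.8 and 24.3 steps/day per day that section 4.2 reports from the earlier trial show scale only; they are not between-person SDs. A false positive on this slope would also suggest waning, not efficacy. No inflation has been shown for the three baseline contrasts.

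**The ANOVA.** It is too strong to say that ANOVA cannot estimate a decline: a linear trend contrast gives an average slope among completers. The figure of 37 also starts from the stated minimum. Section 5.5 anticipates 75 older adults, of whom 75 × 0.75 = 56 would remain. Both qualifications stand.

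**Bias.** Losing less active people does not by itself bias a within-person change; drop-out must be related to the change. If it depends on unobserved steps, a mixed model is biased too. That stands, so the mixed model's advantage is that it uses partial data under a weaker assumption, not that it is immune.

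**Conclusion.** The point holds in conditional form. Section 9.4.2 does not identify one analysis, and the choice affects who is analysed and whether a stated primary hypothesis is tested at its nominal level. Under the ANOVA reading, about 37 of the minimum 50 remain at 25% drop-out. Many more are lost if days are the levels, and few more if phase means are. The daily slope is not estimated by default. Under a random-intercept-only reading, the slope test's error is about 5% with no slope variation or autocorrelation, about 9% to 22% at slope SD 10 to 20, about 11% to 12% at AR(1) 0.2, and higher with both. The slope SD, the autocorrelation and the use of 2,000 as the daily residual SD are assumptions.

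A reader might also infer that the pre-post comparison is underpowered. It is not on these figures: 37 completers give at least 95.6% power under the SDs considered. The issues are an unidentified estimand, possible completer bias and the slope's error rate. For a single-arm pilot this should be corrected, but it does not invalidate the design.

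**What to change.** Remove the reference to repeated-measures ANOVA and specify one linear mixed model:
- **Data:** all available days that meet a stated valid-wear rule.
- **Population:** residents. Alternatively, include employees with resident/employee-by-phase and by-day interactions and make the resident estimates primary. A main effect alone would average the two groups, whereas the primary objective concerns older adults.
- **Fixed effects:** phase (baseline, active, follow-up) and day within the active phase.
- **Random part:** participant intercept and slope, with serially correlated residuals such as AR(1).
- **Estimates:** the three baseline contrasts and the active-phase slope, all from this model.
- **Definitions:** one baseline period, after reconciling the synopsis with section 6.1.1, and one slope window, after repairing the end of the hypothesis in section 9.1.
- **Fallback:** if the model does not converge, t tests on participant-level phase changes and slopes. The slope version kept about 5% error in every setting above.

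The cost is SAP wording and modest programming. Slope intervals will be wider where people differ in their rate of decline, and the fallback may be needed at this sample size.

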9.4.3 ANALYSIS OF THE SECONDARY ENDPOINT(S)

Student's T Test will be used to test the mean scores for social support, self-efficacy, and outcome expectations, and social isolation from baseline to post-intervention. A simple linear regression will be used to examine the linear relationship between changes in psychosocial outcomes and changes in physical activity.

Descriptive statistics (i.e., mean, SD, frequency) and qualitative analysis will be used to analyze acceptability outcomes from the process evaluation.

9.4.4 SAFETY ANALYSES

9.4.5 BASELINE DESCRIPTIVE STATISTICS

Descriptive statistics (i.e., mean, SD, frequency) will be calculated for participant characteristic including age, sex, height, weight, and BMI, education, total annual household income, and length of residence at the retirement community.

9.4.6 PLANNED INTERIM ANALYSES

N/A

9.4.7 SUB-GROUP ANALYSES

9.4.8 TABULATION OF INDIVIDUAL PARTICIPANT DATA

9.4.9 EXPLORATORY ANALYSES

10 SUPPORTING DOCUMENTATION AND OPERATIONAL CONSIDERATIONS

10.1 REGULATORY, ETHICAL, AND STUDY OVERSIGHT CONSIDERATIONS

10.1.1 INFORMED CONSENT PROCESS

Consent forms describing in detail the study intervention, study procedures, and risks are given to the participant and written documentation of informed consent is required prior to starting intervention/administering study intervention. The following consent materials are submitted with this protocol: informed consent, waiver of informed consent.

10.1.1.1 CONSENT/ASSENT AND OTHER INFORMATIONAL DOCUMENTS PROVIDED TO PARTICIPANTS

Informed consent documents will be provided to the participants.

10.1.1.2 CONSENT PROCEDURES AND DOCUMENTATION

A research team member will review the consent document with participants before they sign it. Participants will indicate their consent by signing the consent document. Participants will be provided a copy of the signed consent form to keep for their records. Coercion and undue influence will be minimized by informing the subjects that participation in the study is completely voluntary and that they are free to quit the study at any time without penalty.

10.1.2 STUDY DISCONTINUATION AND CLOSURE

This study may be temporarily suspended or prematurely terminated if there is sufficient reasonable cause. Written notification, documenting the reason for study suspension or termination, will be provided by the suspending or terminating party to [study participants, investigator, funding agency, the Investigational New Drug (IND) or Investigational Device Exemption (IDE) sponsor and regulatory authorities. If the study is prematurely terminated or suspended, the Principal Investigator (PI) will promptly inform study participants, the IRB, and sponsor and will provide the reason(s) for the termination or suspension. Study participants will be contacted, as applicable, and be informed of changes to study visit schedule.

Circumstances that may warrant termination or suspension include, but are not limited to:

- Determination of unexpected, significant, or unacceptable risk to participants
- Demonstration of efficacy that would warrant stopping
- Insufficient compliance of study staff to the protocol (i.e., significant protocol violations)
- Data that are not sufficiently complete and/or evaluable
- Determination that the primary endpoint has been met

Determination of futility

The study may resume once concerns about safety, protocol compliance, and data quality are addressed, and satisfy the funding agency, sponsor, IRB, Food and Drug Administration (FDA), or other relevant regulatory or oversight bodies (OHRP, DSMB).

10.1.3 CONFIDENTIALITY AND PRIVACY

- Paper/hard copy records (hard copy surveys, questionnaires, case report forms, pictures, etc.) Hard copies of informed consent documents will be stored in a secure cabinet located in a laboratory directed by the PI (Field House room E141). The lab is under lock and key and is only accessible to research staff. All participants will be given a unique study ID# which will be linked to collected data. When collecting data at Oaknoll, all documents will be stored in a temporary container in a research team member's possession and then transported to the storage location at the Field House. Databases that include ID numbers and collected data will be stored on a password protected and secure electronic warehouse accessible only to the principal investigator. All collected data will be destroyed 5 years following completion of data analysis.
- Electronic records (computer files, electronic databases, etc.) All data will be collected through a UI Qualtrics account for screening and study data collection. Identifying information that we will collect from participants includes their Name, Address, and Phone Number. The storage of the MapTrek data will be on a password-protected, secure servers in Computer Science Dept. It will only be the participant's phone number and Fitbit data. Only members of the research team will have access to this information through a password protected electronic file on a UI protected server. All collected data will be coded and stored in a password protected electronic file on a UI protected server. These servers are password protected with access only to authorized staff. Folders within the server are also made available to only select staff and with password protection as needed for participant data. A separate list of names with ID#s will be stored in a separate password-protected file for repeated measures comparisons. During the informed consent, we will ask participants for permission to store their data for future use. Participants will be given the option (yes or no) to allow us to store their data. For participants who agree to us storing their data (selecting 'Yes'), we will store that data on our protected server for future analyses. If participants do not agree (select 'No'), we will not store their data and will destroy their electronic data within five years of completion of the study.

10.1.4 FUTURE USE OF STORED SPECIMENS AND DATA

10.1.5 KEY ROLES AND STUDY GOVERNANCE

Principal Investigator	Medical Monitor or Independent Safety Monitor

10.1.6 SAFETY OVERSIGHT 10.1.7 CLINICAL MONITORING 10.1.8 QUALITY ASSURANCE AND QUALITY CONTROL 10.1.9 DATA HANDLING AND RECORD KEEPING 10.1.9.1 DATA COLLECTION AND MANAGEMENT RESPONSIBILITIES 10.1.9.2 STUDY RECORDS RETENTION 10.1.10 PROTOCOL DEVIATIONS 10.1.11 PUBLICATION AND DATA SHARING POLICY 10.1.12 CONFLICT OF INTEREST POLICY 10.2 ADDITIONAL CONSIDERATIONS

10.3 ABBREVIATIONS AND SPECIAL TERMS

AE	Adverse Event	
ANCOVA	Analysis of Covariance	
CFR	Code of Federal Regulations	
CLIA	Clinical Laboratory Improvement Amendments	
CMP	Clinical Monitoring Plan	

COC	Certificate of Confidentiality	
CONSORT	Consolidated Standards of Reporting Trials	
CRF	Case Report Form	
DCC	Data Coordinating Center	
DHHS	Department of Health and Human Services	
DSMB	Data Safety Monitoring Board	
DRE	Disease-Related Event	
EC	Ethics Committee	
eCRF	Electronic Case Report Forms	
FDA	Food and Drug Administration	
FDAAA	Food and Drug Administration Amendments Act of 2007	
FFR	Federal Financial Report	
GCP	Good Clinical Practice	
GLP	Good Laboratory Practices	
GMP	Good Manufacturing Practices	
GWAS	Genome-Wide Association Studies	
HIPAA	Health Insurance Portability and Accountability Act	
IB	Investigator's Brochure	
ICH	International Council on Harmonisation	
ICMJE	International Committee of Medical Journal Editors	
IDE	Investigational Device Exemption	
IND	Investigational New Drug Application	
IRB	Institutional Review Board	
ISM	Independent Safety Monitor	
ITT	Intention-To-Treat	
LSMEANS	Least-squares Means	
MedDRA	Medical Dictionary for Regulatory Activities	
МОР	Manual of Procedures	
NCT	National Clinical Trial	
NIH	National Institutes of Health	
NIH IC	NIH Institute or Center	
OHRP	Office for Human Research Protections	
PI	Principal Investigator	
QA	Quality Assurance	
QC	Quality Control	
SAE	Serious Adverse Event	
SAP	Statistical Analysis Plan	
SMC	Safety Monitoring Committee	
SOA	Schedule of Activities	
SOC	System Organ Class	
SOP	Standard Operating Procedure	

UP	Unanticipated Problem	
US	United States	

10.4 PROTOCOL AMENDMENT HISTORY

Version	Date	Description of Change	Brief Rationale

